5. *Is the use of tranexamic acid cost effective relative to the use of allogenic blood transfusion as a blood loss management strategy in acetabular ORIF?*

A few small previous studies have shown TXA to be cost effective relative to a placebo in orthopaedic patients.[20,26,28] However, the majority of trials have not reported on cost-effectiveness, and meta-analyses on this topic have not been able to draw definitive conclusions on this issue.[8,13,15,19,21,27,35,39] Neither of the two studies in orthopaedic trauma, specifically hip fracture patients, reported on this. [32,40] In this study, we will calculate the cost of tranexamic acid administration in each treatment group, and compare this to the total cost of allogenic blood transfusion in each treatment group. Since TXA is an inexpensive drug, we hypothesize that TXA will be a cost effective blood loss management strategy with acetabular ORIF.

We plan to enroll 50 patients (N=25 treatment, N=25 controls) in a pilot study to test procedures and collect preliminary data. While this pilot study will likely not have sufficient power to definitively address the specific aims and hypotheses, the preliminary data collected will provide information to plan future work.

Study Design:

Eligibility:

Inclusion Criteria: All patients aged 18 or above undergoing acetabular ORIF.

Exclusion Criteria:

- All patients aged below 18 undergoing acetabulum surgery
- Patients with color-blindness (color vision changes used to assess toxicity)
- Patients with subarachnoid hemorrhage.
- Patients with active intravascular coagulation.
- Patients with a previous history of venous thromboembolism or with a history of hypercoagulable conditions (i.e. Factor V Leiden, antiphospholipid antibody).
- Prisoners
- Pregnant women

Patient Consent:

Orthopaedic surgery attendings and residents will identify potential study candidates during the initial consultation based on the presence of an acetabular fracture. If the patient meets the inclusion and exclusion criteria (noted above), a member of the treatment team will discuss the study with eligible patients. If the patient expresses interest in the study, the physician will notify the research staff. Orthopaedic Clinical Research staff will describe study procedures in detail and go through the informed consent process to enroll the patient in the study. The number of eligible patients, and the eventual number enrolled will be specifically reported.

Dosing:

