The study coordinator completing the randomization and the statisticians analyzing the data will not be involved in the treatment of the patient. The Investigational Pharmacy will provide treatment packs that are identical in appearance and differ only by their random number, it will not be possible for either the treating physician, or the patient to know the treatment regimen received.

Unblinding:

In general, it should not be necessary for unblinding to occur. If a contraindication to the treatment regimen develops after randomization (i.e. suspicion of allergic reaction to the treatment), the treating physician will contact the study coordinator immediately to explain the reasons behind the request for unblinding. A thromboembolic event will not be considered a reason for unblinding, as this is a primary outcome measure. However, the rate of thromboembolic events will be monitored and if this rate is noted to be higher than the baseline rate in patients undergoing acetabular ORIF, this will trigger a safety evaluation. Patients whose treatment is unblinded in this manner will be excluded from the final data analysis. The numbers of patients unblinded, and the reasons for the decisions will be specifically reported.

Patient Safety Monitoring

A data safety monitor will be appointed for this study. This person will otherwise be uninvolved in the planning or execution of this trial but will have the ability to unblind the collected data to analyze and determine if subjects experiencing an unacceptably high level of adverse events. There had not been adverse effects of tranexamic acid reported. For this reason, only adverse events outside of what would reasonably be expected for a typical post-operative trauma patient will be considered. These adverse events will be assessed by the treating physicians at every follow-up appointment (2 weeks, 6 weeks, 3 months, and 6 months), who will notify the data safety monitor within 24 hours. If deemed necessary, the data safety monitor will unblind the collected data and determine

if the study group is experiencing adverse events at a significantly higher rate or with greater severity than the control group. If the risk to patients is deemed unacceptably high by the data safety monitor, the study will be terminated and the results will be published.

Sample Size and Feasibility:

Pilot Study:

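### Safety notifications are limited to unexpected adverse events, so nothing in the plan prompts the data safety monitor to review the wound, infection and readmission data already being collected

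*Combined protocol and SAP*

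**What the plan says.** The Patient Safety Monitoring section appoints one independent data safety monitor, who is able to unblind the collected data and end the study if risk is unacceptable. It then narrows what is looked at. It states "There had not been adverse effects of tranexamic acid reported", and for that reason "only adverse events outside of what would reasonably be expected for a typical post-operative trauma patient will be considered". The next sentence carries the restriction forward: the events so defined are assessed by treating physicians at the follow-up visits (2 weeks, 6 weeks, 3 months and 6 months), "who will notify the data safety monitor within 24 hours".

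A comparison between arms is provided for, but only where the monitor judges that unblinding is needed. The question to be answered in that case is "if the study group is experiencing adverse events at a significantly higher rate or with greater severity than the control group".

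Under Blinding, "it will not be possible for either the treating physician, or the patient to know the treatment regimen received". Under Unblinding, a thromboembolic rate above baseline triggers a safety evaluation, and a suspected contraindication is reported to the study coordinator. Under Data Collection, the coordinator divides the data by treatment group and passes them to the statisticians for the analysis. Items 11 and 13-16 cover readmission, wound infection, dehiscence, return to the OR and all bacterial infection.

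**The concern.** Harm that takes the form of more of an ordinary complication is hard to recognise one patient at a time. A single wound infection after acetabular fixation looks unremarkable; what would be informative is a count that differs between arms or is higher than it should be. The people who notify the monitor cannot see arm, and the rule tells them to pass on only what is out of the ordinary.

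Wound complications are research question 4. The protocol hopes TXA reduces them and says this has not yet been shown in orthopaedics, so the direction of effect is open. If it were unfavourable, the monitor could find out by choosing to look, but nothing in the plan would lead to that choice. The pilot is also meant to inform a larger study, which could inherit the rule.

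**Working it through.** **Step 1: trace each event type to the monitor.**

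| Event type | Collected? | What brings it to the monitor |
|---|---|---|
| Unexpected adverse event | Not a listed data point | Physician notification within 24 hours |
| DVT, PE, MI, stroke (item 12) | Yes | Thromboembolic events have a rate trigger for a safety evaluation |
| Contraindication, such as suspected allergy | Through unblinding requests | Goes to the coordinator |
| Readmission, wound infection, dehiscence, return to the OR, bacterial infection (items 11, 13-16) | Yes | Nothing stated; the data go to the statisticians for the analysis |

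The last row is the gap. Reading the restriction to include unusual frequency does not close it, because blinded physicians reporting single patients cannot see an imbalance by arm.

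**Step 2: inputs for scale.** The plan states no figure for this rule, so there is none to reproduce. Pilot size is 25 per arm, and the infection rate is 2-5% in general populations (both from Sample Size and Feasibility). The same section gives up to 15% in morbidly obese patients, which is not used below. Two assumptions are added: TXA doubles the risk, and an interim look falls at 12 per arm. The documents give no rates for dehiscence, return to the OR or readmission, so those are not quantified.

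**Step 3: expected counts.**
- Both arms with no effect: 50 × 0.02 = 1.0 and 50 × 0.05 = 2.5.
- At least one infection in 50: 1 − 0.98^50 = 0.64 and 1 − 0.95^50 = 0.92.
- Under doubling, TXA: 25 × 0.04 = 1.0 and 25 × 0.10 = 2.5. Placebo: 25 × 0.02 = 0.5 and 25 × 0.05 = 1.25.

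**Step 4: chance that TXA has at least two more infections than placebo.** With independent binomial counts, sum P(placebo = a) × P(TXA = b) over all b ≥ a + 2.

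| Per arm | Placebo rate | TXA rate doubled | No effect |
|---|---|---|---|
| 25 | 2% | 0.18 | 0.06 |
| 25 | 5% | 0.44 | 0.15 |
| 12 (assumed) | 2% | 0.07 | 0.02 |
| 12 (assumed) | 5% | 0.22 | 0.07 |

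**Step 5: could a significance test do the job?** Two-sided Fisher test, 25 per arm: 5 v 0 gives p = 0.0502 and 6 v 0 gives p = 0.022. Summing the probabilities of all tables with p < 0.05 and more events on TXA, under doubling, gives 0.0002 at 2% and 0.013 at 5%. A test would almost never signal, so the counts can only inform judgement.

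**The case against.** **The monitor's powers are not limited.** This stands. The monitor may unblind all collected data, and items 11 and 13-16 are collected data. A reader might infer that expected complications are barred from safety review, or that the monitor is obliged to compare arms and has been denied the data. The text supports neither: the comparison is conditional, and what is missing is a prompt.

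**The protocol lists no expected events.** This also stands. An unusually severe infection could be notified under the present wording. Classing these complications as expected is an inference, reasonable for infection given the quoted background rates and weaker for the other items.

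**Pooled counts could be checked against a baseline without unblinding**, as is planned for thromboembolism. That is possible for infection, but weak. If TXA doubled a 2% rate, the pooled expectation would be 0.5 + 1.0 = 1.5 in 50, or 3%, still inside the quoted 2-5%. If it doubled a 5% rate, the expectation would be 1.25 + 2.5 = 3.75, or 7.5%. A coded-arm table carries more information for similar effort.

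**The end-of-pilot figures flatter an interim table.** They do; the 12-per-arm rows in the working are the fairer guide to what could be seen while patients are still being enrolled.

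**The stated premise is a side issue.** Largely so. The claim that no adverse effects had been reported sits badly with the exclusion criterion "Patients with color-blindness (color vision changes used to assess toxicity", and the two should be reconciled. A reader might take this as evidence that wound harms are being missed. It is not: a colour vision change would hardly be expected after trauma surgery, so the present rule would notify it.

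**Monitor review might exclude patients.** One might infer this from "Patients whose treatment is unblinded in this manner will be excluded from the final data analysis". In context, that sentence most naturally concerns individual requests from treating physicians.

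**Conclusion.** The concern holds as a procedural gap. Followed as written, the rule keeps ordinary wound, infection and readmission events out of the notifications that would lead the monitor to look, and no scheduled report or trigger makes up for it. It does not show that review is prohibited or that harm would go unseen.

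The practical size within a 50-patient pilot is modest. At an assumed 12 per arm and an assumed doubling of a 2-5% infection rate, an excess of two or more on TXA would appear with probability about 0.07-0.22, against 0.02-0.07 by chance alone. The conclusion rests on reading infection and similar complications as expected events. The sponsor should correct the text because the rule is explicit, the change is cheap, and the pilot may lead to a larger trial.

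**What to change.** 1. Delete the sentence restricting consideration to unexpected events, and reconcile its stated reason with the colour-vision exclusion criterion.
2. Have the study coordinator, who is not involved in treatment and already divides the data by group, send the independent monitor a tabulation of items 11 and 13-16 by coded arm on a stated schedule. The monitor can unblind the codes; treating physicians and patients stay blinded.
3. State that the tables inform the monitor's judgement and are not a significance test, and reword the criterion of a significantly higher rate to match.

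**Cost:** protocol wording and a little tabulation, since the items are already collected and a monitor with unblinding rights is already planned. The downside is more routine by-arm review by the monitor, with small counts that will sometimes differ by chance.
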